10.4.4 Pharmacokinetic Endpoints and Analyses

The PK endpoints with Q1W dosing will be derived based on the concentration time curves of Pan-HER after the first and fourth infusion of Pan-HER in both parts of the trial, as applicable.

The PK endpoints with Q2W dosing will be derived based on the concentration time curves of Pan-HER after the first and third infusion of Pan-HER in both parts of the trial, as applicable. Refer to **Table 13**. The serum concentration of total Pan-HER will be derived as the sum of the serum concentration of all six constituting antibodies. Supporting plots and PK parameters for the individual antibodies will also be generated.

Confidential Page 99 of 156

Table 13 Pharmacokinetic (PK) Endpoints, Definitions, and Derivations

Symbol	Definition and derivation
Ctrough	Trough concentration (i.e., concentration of Pan-HER measured pre-infusion)
$\mathrm{AUC}_{ au}$	Area under the concentration-time curve in a dosing interval (i.e., from time zero (end of infusion) up to 168 hours). AUC $_{\tau}$ will be calculated using the linear trapezoidal method and interpolated in case of measurements after 168 hours, or extrapolated using terminal rate constant and the last quantifiable concentration
$\mathrm{AUC}_{ au0}$	Area under the concentration-time curve from start of infusion up to 168 hours. $AUC_{\tau0}$ will be calculated similar to AUC_{τ}
$AUC_{norm,\tau}$	Dose normalized area under the concentration-time curve in a dosing interval, calculated as AUC $_{\tau}$ divided by the dose infused
C _{max}	Maximum concentration
T_{max}	Time to reach maximum concentration
C _{EOI}	Concentration at End of Infusion
$\lambda_{\rm z}$	Terminal rate constant (negative of the slope of an In-linear regression of the un-weighted data considering the terminal phase of the concentration-time curve \geq limit of quantification). λ_z is not an endpoint, but is used for derivation of endpoints
T _{1/2}	Terminal elimination half-life, calculated as $ln(2)/\lambda_z$
CL _S	Clearance after first dose, calculated as Dose/AUC $_{inf}$ for C1/D1, where AUC $_{inf}$ will be calculated as the sum of the area from time zero to time of last quantifiable concentration, t_z , and the area from t_z to infinity. The second area will be estimated using the observed concentration at t_z and the terminal rate constant
$\mathrm{CL}_{\mathrm{SS}}$	Clearance after 4^{th} dose, calculated as Dose/AUC $_{\tau}$

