Statistical Analysis Plan Template for Early Phase Studies

Symphogen A/S
 Sym013-01

The planned PK endpoints are listed in Table 13 of Clinical Study Protocol.

The data may not allow for derivation of all endpoints for all mAbs, patients and occasions. C_{max} , C_{EOI} , C_{trough} and T_{max} will be derived from observed data while AUC_{τ} , $AUC_{\tau 0}$, $AUC_{norm, \tau}$, CL_s , CL_{ss} , V_s , V_{ss} , and $T_{1/2}$ will be estimated using non-compartmental methods and actual time points.

Table 13 Pharmacokinetic (PK) Endpoints, Definitions and Derivations

Symbol	Definition and derivation
C_{trough}	Trough concentration (i.e. concentration of Pan-HER measured pre-infusion)
AUC_{τ}	Area under the concentration-time curve in a dosing interval (i.e. from time zero (end of infusion) up to 168 hours). AUC_{τ} will be calculated using the linear trapezoidal method and interpolated in case of measurements after 168 hours, or extrapolated using terminal rate constant and the last quantifiable concentration
$AUC_{\tau 0}$	Area under the concentration-time curve from start of infusion up to 168 hours. $AUC_{\tau 0}$ will be calculated similar to AUC_{τ}
$AUC_{norm, \tau}$	Dose normalized area under the concentration-time curve in a dosing interval, calculated as AUC_{τ} divided by the dose infused
C_{max}	Maximum concentration
T_{max}	Time to reach maximum concentration
C_{EOI}	Concentration at End of Infusion
λ_z	Terminal rate constant (negative of the slope of an ln-linear regression of the un-weighted data considering the terminal phase of the concentration-time curve \geq limit of quantification). λ_z is not an endpoint, but is used for derivation of endpoints

PAREXEL International
Statistical Analysis Plan Template for Early Phase Studies

Symphogen A/S
 Sym013-01

Symbol	Definition and derivation
$T_{1/2}$	Terminal elimination half-life, calculated as $\ln(2)/\lambda_z$
CL_s	Clearance after first dose, calculated as Dose/AUC _{inf} for C1/D1, where AUC _{inf} will be calculated as the sum of the area from time zero to time of last quantifiable concentration, t_z , and the area from t_z to infinity. The second area will be estimated using the observed concentration at t_z and the terminal rate constant
CL_{ss}	Clearance after 3 rd /4 th dose, calculated as Dose/AUC _{τ}
V_s	Volume of distribution during the terminal phase after first dose (CL_s/λ_z)
V_{ss}	Volume of distribution during the terminal phase after 3 rd /4 th dose (CL_{ss}/λ_z)

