4.10.4.3 Pharmacokinetic Parameters

Pharmacokinetic parameters for the first and second PK profile (as defined in 4.10.4.1) for each patient and each monoclonal antibody will be derived by model-independent, non-compartmental analysis (NCA) according to Symphogen's local procedures.

All derived serum PK parameters will be listed by mAb, dose schedule, dose group, patient, and actual time point (Listing 16.2.6.2.1-2) and summarized descriptively by mAb, dose schedule and group and day (Table 14.2.2.1-2). The following descriptive statistics will be presented for PK parameters: n, arithmetic mean, SD, geometric mean, geometric CV% (calculated as: $gCV\% = \text{SQRT}(\exp(s^2) - 1) * 100$; where s is the standard deviation of the log-transformed values), median, minimum and maximum values.

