4.14 Changes in the Conduct of the Study or Planned Analysis

The trial has been stopped during Part 1, no patient is enrolled in Part 2. Part 2 of the trial did not take place.

- Objectives for Part 2 are omitted. Per protocol, the concentration of total Pan-HER (the sum of the serum concentration for all six mAbs) was planned to be used for the PK analysis. However, in an exploratory analysis, the PK of the six mAbs was shown not to be similar, and hence using the sum of concentrations is not justified. Hence, the PK of each mAb is reported;
- Overall Survival was planned as one of the Protocol Endpoints, this analysis will not be performed: patients in this study are not followed up to death so that OS would result in a truncated biased estimate;
- Time to documented PD, death, patient withdrawal or end of trial participation, whichever comes first was initially planned in the Protocol Endpoints. Actually, based on FDA guideline as of December 2018 [3], TTP is mentioned as a possible endpoint for oncological studies, '*TTP is defined as the time from randomization until objective tumor progression; TTP does not include deaths.*' TTP will be used as an endpoint in this study instead of the planned time to documented PD, death, patient withdrawal or end of trial participation.
- Duration of SD was initially planned in the Protocol Endpoints, anyway this endpoint is overlapping with TTP being derived in a very similar way; thus, this endpoint will not be part of the data analysis.
- DCR analysis was not included as part of study endpoints in the Protocol, such analysis has been added in this SAP.

Given the early interruption of the trial, Symphegen decided to proceed with an abbreviated Clinical Study Report; from list of Tables, Figures and Listings reported in below section 6, only those flagged with asterisk (*) will be produced for the abbreviated CSR.

PAREXEL International
Statistical Analysis Plan Template for Early Phase Studies

Symphogen A/S

Sym013-01

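### SAP Table 13 does not say which dose applies to a single mAb; read literally, per-mAb clearance, volume and dose-normalised AUC would be off by the inverse of that mAb's mass share

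*SAP*

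**What the plan says.** Protocol section 10.4.4 makes total Pan-HER the main analyte: "The serum concentration of total Pan-HER will be derived as the sum of the serum concentration of all six constituting antibodies". It adds the components as supporting output: "Supporting plots and PK parameters for the individual antibodies will also be generated". Its Table 13 is the only table of parameter definitions for either purpose.

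SAP section 4.14 drops the total because an exploratory analysis found that the six antibodies behave differently: "hence using the sum of concentrations is not justified. Hence, the PK of each mAb is reported". SAP section 4.10.4.3 accordingly says that parameters "for each patient and each monoclonal antibody will be derived by model-independent, non-compartmental analysis", and refers to the sponsor's local procedures for how this is done.

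SAP Table 13 keeps the protocol's dose-dependent definitions:

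- CLs: "Clearance after first dose, calculated as Dose/AUC" extrapolated to infinity.
- CLss: dose over AUCtau.
- Vs: "Volume of distribution during the terminal phase after first dose", computed as CLs over lambda_z; Vss is the same with CLss.
- AUCnorm,tau: AUCtau "divided by the dose infused".

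The table was revised in other respects: the repeat-dose parameters now refer to the third or fourth dose, where the protocol had only the fourth. The trough row still describes a concentration of Pan-HER.

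**The concern.** Dose over AUC is a clearance only when both terms describe the same material. For total Pan-HER they do. For one antibody, the AUC reflects only that antibody's part of the infusion, so the numerator must be that part of the dose.

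Neither document defines a component dose, a mass fraction or a scaling step. Sites record the total dose and volume of each infusion (protocol 7.1.3.1), dosing is in mg/kg of Pan-HER (protocol 7.1.4 and 7.1.4.1), and the SAP's exposure derivations (4.9) use the same quantity. A programmer working from Table 13 alone would have only the whole-mixture dose to divide by.

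At stake are five parameters (CLs, CLss, Vs, Vss, AUCnorm,tau) for six antibodies in Table 14.2.2 and Listing 16.2.6.2. Both outputs are flagged in SAP section 6 for the abbreviated report. With the total dropped, they hold the only clearance, volume and dose-normalised results the SAP plans.

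**Working it through.** The documents state no numerical result here, so there is no figure to reproduce. The check is algebraic.

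**Inputs**

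- D: the Pan-HER dose infused, the only dose recorded (protocol 7.1.3.1).
- Six antibodies in the mixture (SAP section 1).
- f: the mass share of one antibody. It is not stated. Protocol section 7.1 gives only the overall strength, 12 mg/mL. Values of f below are assumptions.

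**Formulas for one antibody**

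| Parameter | With the component dose f·D | Table 13 read literally, with D | Literal ÷ component |
|---|---|---|---|
| CLs | f·D / AUCinf | D / AUCinf | 1/f |
| CLss | f·D / AUCtau | D / AUCtau | 1/f |
| Vs, Vss | CL / lambda_z | inflated CL / lambda_z | 1/f |
| AUCnorm,tau | AUCtau / (f·D) | AUCtau / D | f |

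**Numerical illustration.** Assume D = 9 mg/kg, f = 1/6, volume 0.06 L/kg and half-life 48 h.

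- Component dose: 9/6 = 1.5 mg/kg.
- lambda_z = ln 2 / 48 = 0.01444 per h.
- True CL = 0.01444 × 0.06 = 0.000866 L/h/kg.
- AUCinf = 1.5 / 0.000866 ≈ 1731 mg·h/L.
- Literal CL = 9 / 1731 = 0.00520 L/h/kg, which is 6 times the true value.
- Literal V = 0.00520 / 0.01444 = 0.36 L/kg, also 6 times the true value.
- Dose-normalised AUC comes out at 1/6 = 0.167 of its proper value.

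The assumed dose, volume and half-life cancel; the ratios depend on f alone.

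**Range over assumed shares**

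| f | CL and V too high by | AUCnorm,tau at this fraction of its value |
|---|---|---|
| 25% | 4-fold | 0.25 |
| 1/6 (equal shares) | 6-fold | 0.167 |
| 10% | 10-fold | 0.10 |

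**Comparisons between antibodies.** With equal shares, every antibody carries the same multiplier and the ranking is preserved. With unequal shares it is not: two antibodies at 10% and 25% with identical true clearance would appear 10/4 = 2.5-fold apart.

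**What is untouched.** Cmax, C_EOI, Ctrough, Tmax, AUCtau, AUCtau0, lambda_z and T1/2 do not use the dose. Comparisons of one antibody across dose groups, schedules or occasions hold if its share is constant. For the total, D divided by the summed AUC stays coherent.

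**The case against.** The strongest reply is that the SAP never instructs anyone to divide by the mixture dose. *Dose* is undefined, SAP 3.2.3 introduces the table as serving all the antibodies, and section 4.10.4.3 hands the non-compartmental analysis to local procedures that may scale the dose by component. This stands in part. A reader might infer that every per-mAb value will be wrong; the documents do not show that, because the procedures that decide it are not included. It does not remove the defect. If those procedures scale the dose, they do something Table 13 does not say; if they do not, the values are wrong.

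A reader might also infer that the SAP's change of analyte created the gap. It did not. Protocol 8.4 already has the six individual concentrations supporting the PK endpoints, and protocol 10.4.4 already planned component parameters under the same table. What the SAP changed is their standing, from supporting output to the only output.

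It might further be inferred that the stated reason for leaving the total, dissimilar PK among the six, is an artefact of this division. Nothing supports that: section 4.14 cites an earlier exploratory analysis and does not tie it to these parameters.

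The consequences are also limited. PK is a secondary objective, all analyses are descriptive (SAP 4.10.1.2), Part 2 did not take place, and no stated decision depends on per-mAb clearance or volume. With known, constant shares, any error is a fixed multiplier that could be corrected afterwards. These points lower the severity; they do not make the written formula right.

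**Conclusion.** The point holds as a conditional one. SAP Table 13 gives dose-dependent formulas suited to total Pan-HER, while the SAP now reports only individual antibodies, and the one infused dose the documents define is that of the whole mixture. Applied literally, the formulas inflate CLs, CLss, Vs and Vss by 1/f and reduce AUCnorm,tau to f of its value for all six antibodies, since every share is below 1.

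The size rests on shares the documents do not give. The 6-fold figure assumes equal parts and should not be read as a finding about this product; 4- to 10-fold corresponds to assumed shares of 25% to 10%. Whether any reported value would be wrong depends on the unseen local procedures. Between-antibody comparisons of these parameters are distorted only if shares are unequal.

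This should be fixed before Table 14.2.2 and Listing 16.2.6.2 are produced. It has no effect on the primary DLT endpoint.

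**What to change.** In SAP Table 13:

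1. For each antibody, define the dose in CLs, CLss and AUCnorm,tau (and so in Vs and Vss) as the actual Pan-HER dose infused multiplied by that antibody's mass fraction in the drug product.
2. State the six fractions used and their source. Use the nominal composition, or batch-specific values where a batch can be linked to the infusion. The fix should not depend on that link: the dosing history in protocol 7.1.3.1 lists no batch number, and batch numbers appear only in the accountability records of protocol 7.4, as applicable.
3. In the trough row, refer to the concentration of the mAb instead of Pan-HER.
4. If the local NCA procedures already scale the dose, say so in section 4.10.4.3 and make Table 13 agree with them.

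The cost is a few lines of SAP text and the sponsor's composition figures, which the documents do not contain. No new patient data are needed.

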3.2.4 Safety Variables

The following safety endpoints will be assessed:

- Dose-Limiting Toxicities Evaluation
- (S)AE Survey
- Prior and concomitant medications (medications and/or treatments taken other than Pan-HER)
- Laboratory assessments (biochemistry, hematology, urinalysis, and coagulation)
- Pregnancy test
- 12-lead electrocardiogram (ECG)

PAREXEL International
Statistical Analysis Plan Template for Early Phase Studies

Symphogen A/S

Sym013-01

- Echocardiogram (ECHO) or Multi-Gated Acquisition (MUGA) Scan
- Vital Signs and Body Measurements
- Physical Examination
- Eastern Cooperative Oncology Group (ECOG) performance status (PS) score

3.2.4.1 Dose Limiting Toxicity

A DLT is defined as any of the following toxicities that occur during the DLT-observation period, if considered related (causality rating of possibly, probably, or related) to Pan-HER:

1. Grade 3 non-hematologic toxicity regardless of duration, with the exception of:
 - a. Grade 3 nausea, vomiting, diarrhea, or fatigue lasting ≤ 2 days with best supportive care
 - b. Grade 3 asymptomatic electrolyte abnormality that is not considered clinically significant by the Investigator and that is controlled with medical therapy
2. Grade 4 non-hematologic toxicity, with the exception of:
 - a. Grade 4 asymptomatic electrolyte abnormalities that is not considered clinically significant by the Investigator and that is controlled with medical therapy
3. Neutropenia that is:
 - a. Grade 3-4 febrile neutropenia
 - b. Grade 4 and sustained (i.e., ANC $<0.5 \times 10^9/L$ [500/mm³], duration >5 days)
4. Thrombocytopenia that is
 - a. Grade 3 with clinically significant hemorrhage
 - b. Grade 4 (platelets $<25 \times 10^9/L$ [25,000/mm³])
5. AST/ALT elevation $>3 \times ULN$ with bilirubin elevation $>2 \times ULN$ without evidence of cholestasis that cannot be explained by factors not related to Pan-HER

PAREXEL International
Statistical Analysis Plan Template for Early Phase Studies

Symphogen A/S

Sym013-01

6. Evidence of cardiac toxicity as defined by either:
 - a. $\geq 16\%$ absolute decrease in LVEF from baseline, or
 - b. LVEF below the institutional lower limit of normal and $\geq 10\%$ absolute decrease in LVEF from baseline
7. Inability to complete Cycle 1 at the assigned dose due to \geq Grade 3 toxicity
8. Treatment delays >2 weeks from the scheduled next dose due to \geq Grade 3 toxicity

DLT events (Yes / No) are collected in CRF as well as date of assessment, DLT description and AE Reference.

The decision to dose-escalate will be based on close monitoring of safety during the observation period for DLTs, defined as the initial 28-day period (± 2 days) from first treatment of Pan-HER (i.e. Cycle 1) and including 7 days for Q1W or 14 days for Q2W of follow-up from the last dose of Cycle 1.

A minimum of 4 infusions of Pan-HER (Q1W dosing) or 2 infusions of Pan-HER (Q2W dosing) must have been administered at the assigned dose for a patient to have completed the DLT-observation period.

3.2.4.2 Adverse Events

Definitions

An Adverse Event (AE) is any untoward medical occurrence in a patient or a clinical investigation patient administered a pharmaceutical product, and which does not necessarily have a causal relationship with this treatment. An AE can therefore be any unfavorable and unintended sign (including an abnormal laboratory finding), symptom, or disease temporally associated with the use of an IMP, whether or not considered related to the IMP.

Treatment-emergent AEs are events that occur on or after first dose of the study medication or a worsening in severity of a preexisting condition occurring on or after first dose of the study

PAREXEL International
Statistical Analysis Plan Template for Early Phase Studies

Symphogen A/S

Sym013-01

medication (a pre-existing is a condition that is present before the AE recording period starts and is noted on the medical history/physical examination form).

An IRR is defined as an AE occurring during the Pan-HER infusion and up to 2 hours after the end of infusion (EOI), which is assessed by the Investigator as possibly, probably, or related to Pan-HER; IRRs (Yes/No) will be captured in CRF.

AE duration will be derived as AE duration = (AE end date - AE onset date +1); in case of AE ongoing, the date of last contact with the patient will be used as AE for the scope of derive the AE duration.

An SAE is an AE that meets one or more of the following outcome criteria:

- Results in death
- Is life-threatening (patient is at immediate risk of death at the time of the event; it does not refer to an event which hypothetically might cause death if it was more severe)
- Requires in patient hospitalization (formal admission to a hospital for medical reasons) or prolongation of existing hospitalization
- Results in persistent or significant disability/incapacity
- Results in a congenital anomaly/birth defect
- Is medically important (Medically important events may not be immediately life-threatening or result in death or hospitalization but may jeopardize the patient or may require intervention to prevent one of the other outcomes listed in the definition above)

All AEs will be recorded from signing of informed consent for participation in the trial. The recording period ends at the time of the 1M FUP Visit.

All referenced toxicity grading within this protocol will be according to the CTCAE v4.03. If the severity of an AE is not specifically graded by the CTCAE guidance document, the Investigator should use the general definitions of Grades 1 to 5 as per the following, and use his/her best medical judgment to describe the severity of the AE:

PAREXEL International
Statistical Analysis Plan Template for Early Phase Studies

Symphogen A/S

Sym013-01

- Grade 1: Mild
- Grade 2: Moderate
- Grade 3: Severe
- Grade 4: Life-threatening or disabling
- Grade 5: Death caused by the event

Changes in severity of AEs will be recorded.

AEs will be assessed for causal relationship to the IMP. The causal relationship of an AE to the IMP, Pan-HER, will be rated as follows:

- Not Related (The AE is not related to the IMP)
- Unlikely Related (The AE is considered not related to the IMP)
- Possibly Related (The AE might not be related, but possibility cannot be ruled out with certainty and therefore would be considered related)
- Probably Related (It has been determined with a high degree of certainty that the AE is associated with administration of IMP)
- Related (The AE is related to the IMP)

Outcome of the AE will be assessed utilizing one of the following terms:

- Recovered
- Recovered with sequelae (if recovered with sequelae, specify sequelae)
- Not recovered
- Fatal
- Unknown

PAREXEL International
Statistical Analysis Plan Template for Early Phase Studies

Symphogen A/S

Sym013-01

Handling of partial AE onset and end date

Any AEs with incomplete start and end dates will be treated as follows:

- Adverse events with completely unknown onset date will be considered as treatment-emergent; for the scope of AE duration derivation, these AE will be considered as occurred the day of first IMP infusion.
- Adverse events with unknown start day and month but with known start year will be considered:
 - as treatment-emergent if the start year coincides or is after the first dosing year; for the scope of AE duration derivation, these AE will be considered as occurred the day of first IMP infusion if the start year coincides with first dosing year, as occurred on 1st January otherwise (i.e. in case the start year is after the first dosing year)
 - as non-treatment emergent if start year is before the first dosing year; for the scope of AE duration derivation, these AE will be considered as occurred on 1st January.
- Adverse events with unknown start day but with known start month and year will be considered:
 - as treatment-emergent if the start month and year coincide or are after the month and year of first dosing; for the scope of AE duration derivation, these AE will be considered as occurred the day of first IMP infusion if the start month and year coincides with first dosing month and year, as occurred on 1st day of the month otherwise (i.e. in case the month and year is after the month and year of first dosing)
 - as non-treatment emergent if start month and year is before the month and year of first dosing; for the scope of AE duration derivation, these AE will be considered as occurred on 1st day of the month.
- Adverse events with completely unknown end date will be considered as ended on the day of last contact with the patient).

PAREXEL International
Statistical Analysis Plan Template for Early Phase Studies

Symphogen A/S
Sym013-01

- Adverse events with unknown end day and month but with known end year:
 - if the AE end year is before the year of last contact with the patient, AE will be considered as ended on 31th December.
 - if the AE end year coincide with the year of last contact with the patient, AE will be considered as ended on day of last contact with the patient.
 - If AE end year is after the year of last contact with the patient, for the scope of derive the AE duration the date of last contact with the patient will be used as AE end date.
- Adverse events with unknown end day but known end month and end year:
 - if the AE end month and year are before the month and year of last contact with the patient, AE will be considered as ended on last day of the month.
 - if the AE end month and year are coinciding with the month and year of last contact with the patient, AE will be considered as ended on last day of last contact with the patient.
 - If AE end month and year are after the month and year of last contact with the patient, for the scope of derive the AE duration the date of last contact with the patient as AE end date.

Adverse events with completely or partial unknown start and end dates will be shown as not known (NK), for the respective unknown part, in the listings.

